13.1.7. Pharmacoeconomic and Health Outcomes Endpoints

Sufficient data will be collected on resource utilization and quality of life to undertake cost-effectiveness analyses that are relevant to the major countries taking part in this study. Resource utilization data on hospitalizations, healthcare provider visits, and medications will be combined with appropriate national unit costs to calculate a cost per patient per year in the study.

Quality of life data from patient-reported outcomes measures will be combined with survival data to calculate quality adjusted time in the study per patient. Cost-effectiveness analyses will report the incremental cost per major clinical outcome averted, liver-related death averted,

life-year gained and quality-adjusted life year gained, including OCA as part of usual care versus usual care without OCA. Analyses will be conducted within the study and using a lifetime perspective. A separate economic analysis plan will be prepared and reported separately from this protocol.

13.1.8. Supportive Analysis

Per the International Conference on Harmonisation (ICH) E10 guidance, “where no obvious single optimal external control exists, it may be advisable to study multiple external controls”. In order to address the risks associated with the inclusion of a long-term placebo arm, supportive analyses of the primary endpoint will compare clinical outcomes in the OCA treatment arm to historical controls.

In an attempt to avoid the inherent biases with historical controls and to maintain the integrity of this comparison, one can invoke matching methods to optimize comparability and find a historical control that is “similar” to a participating subject. The historical database control should be as similar as possible to the study population and should have been exposed to a similar standard of care (see [Section 5.5.2.3](#)).

A propensity score can be used to reduce bias through matching, stratification, regression adjustment, or some combination. Propensity scores use information from a pool of patients who do not participate in the study (historical controls) to identify what would have happened to participating subjects in the absence of the treatment. By comparing how outcomes differ for treated subjects relative to historical controls, it is possible to estimate the effects of the treatment.

Although it might be relatively simple to assign a historical control based on a single observable characteristic, in practice, if the matching process is to successfully mitigate potential bias, it has to be done considering a full range of covariates across which the treatment and historical controls might differ. Although the results of using matching controls are conditional only on the observed covariates, if one has the ability to measure many of the covariates that are believed to be related to the treatment assignment, then one can be fairly confident that approximately unbiased estimates for the treatment effect can be obtained. Both UK-PBC Group and the Global PBC Study Group formally collect numerous covariates that could be used for propensity score estimation including standard of care, eg, UDCA.

Historical controls will be chosen based on the same inclusion/exclusion criteria where possible.

Propensity scores will be estimated using the available covariates that predict receiving the treatment. Only covariates and not outcome variables will be included in the propensity score estimation. Therefore, there is no chance of biasing results in favor of one treatment.

The covariates and factors collected in the historical databases will be specified in the SAP.

Propensity scores will be estimated first through a logistic regression model with treatment group as the dependent variable and the above covariates/factors as independent variables. Then the stratum boundaries are determined based on the propensity score values for both groups (OCA population and control [historical and randomized placebo]) combined or in the OCA population or historical control group alone. Based on recommendations in the literature, quintiles of the

estimated propensity score from the combined group will be used to determine the stratum boundary cut-offs for the different strata.

Outcome events collected in the historical database are: death (liver-related and all-cause), liver transplant, hepatocellular carcinoma, and other. Other is defined as cirrhosis or decompensation such as ascites, variceal bleed, and encephalopathy.

The propensity score quintile will be then be used as the stratification factor in the stratified log rank test to compare randomized OCA-treated subjects in the ITT population and historical controls (Overall Historical Control Population: both the UK-PBC Group and Global PBC Study Group databases) on the following outcomes:

- Time to death (all-cause)
- Time to liver-related death
- Time to liver transplant
- Time to liver transplant or death (all-cause)
- Time to liver transplant or liver-related death
- Time to hepatocellular carcinoma

KM estimates of the distribution of the time-to-event will be tabulated and graphed by treatment group. The tabulation will include the KM estimate of the medians and corresponding 95% CIs if the medians can be estimated. The number and percent of subjects censored and with events will be presented. The hazard ratio and 95% CI will be determined based on a Cox regression model stratified by randomization strata to estimate the magnitude of the effect.

Sensitivity analyses will be conducted limiting to the separate individual historical control databases, ie, UK-PBC Group and Global PBC Study Group. To evaluate the robustness of the propensity score estimations, additional algorithms and factors may be considered.

Although the study is designed as a placebo-controlled study, the DMC may recommend changes to study conduct based on the pre-specified interim analyses (see [Section 13.1.12](#)), including the potential use of a revised primary efficacy analysis. This analysis would compare all subjects in the OCA population, to all control subjects (randomized placebo and historical controls) on time to liver transplant or death (all-cause), using similar statistical methodology as specified above.

Notably, the planned primary analysis would not be revised without prior agreement with regulatory authorities.

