13.1.2. Determination of Sample Size

The following assumptions were used in sample size calculations:

- Exponential survival curves, placebo survival estimate of 0.6 at 8 years with a hazard ratio of 0.60, and total study duration of 10 years (from first subject enrolled), allowing for 4 years subject accrual and 6 years of follow up.
- Subjects will be randomized in a 1:1 ratio to placebo or OCA.
- The 2 groups will be compared using a 2-sided log rank test at the 5% level of significance.
- Two interim analyses and one final analysis are planned.

Based on the randomization ratio, significance level, and assumed hazard ratio, a total of 127 events (both groups combined) will provide 80% power to demonstrate a statistically significant difference between OCA and placebo on time to liver-related outcomes, including all-cause mortality.

In addition, based on the remaining assumptions stated above, it is estimated that approximately 428 subjects will be enrolled to attain 127 events.

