13.1.5. Additional Secondary Efficacy Analyses

The following time to event secondary efficacy analyses will compare randomized OCA versus randomized placebo using the ITT population:

- Time to each component of the primary efficacy endpoint (except MELD score ≥ 15 which is captured above)
- Time to development of varix/varices
- Time to liver-related death
- Time to liver-related death or liver transplant
- Time to liver-related death, liver transplant, or MELD score ≥ 15

The same analysis methodology as used for the primary efficacy analysis will be used for these secondary efficacy analyses. Similar endpoints, where available, will be analyzed to compare OCA to historical controls as described below in [Section 13.1.8](#).

Analyses of changes in liver biochemistry (GGT, ALT, AST, conjugated bilirubin, albumin, and INR) will be summarized and analyzed using the same methodology as specified in [Section 13.1.4](#) for the key secondary analyses of change in ALP and total bilirubin.

Progression to cirrhosis will be assessed in the subset of subjects considered non-cirrhotic at baseline using available medical history, clinical, and laboratory assessments as well as baseline TE, where available. Specifically, subjects with no clinical, laboratory, or radiological evidence of cirrhosis at baseline and/or a TE liver stiffness of < 16.9 kPa ([Corpechot 2012](#)) will be considered non-cirrhotic (See [Section 9.7.3.1](#)). Progression to cirrhosis will be assessed by the development of clinical, laboratory, or radiological evidence of cirrhosis and/or when liver stiffness increases to ≥ 16.9 kPa during the trial in which case histological progression to cirrhosis should be confirmed by biopsy unless not medically indicated. Using this definition for progression to cirrhosis, the percentage of non-cirrhotic subjects progressing to cirrhosis during the treatment period will be summarized by treatment group and compared using a Cochran–Mantel–Haenszel test stratified by the randomization stratification factor.

Analyses for the histological assessment conducted as part of the biopsy sub-study are defined in [Appendix C](#)).

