13.1.9.1. Time to Event Endpoints

For the time to event analyses, subjects who do not experience an event will be censored at the time of their last contact. Subjects with no data after randomization will be considered to have an event on Day 1 (first day of investigational product dosing).

For analyses of the percentage of subjects with an event, subjects with no data after randomization will be considered to have an event.

All time to event endpoints include only adjudicated events. Sensitivity analyses may consider all events regardless of adjudication. Events with discrepant adjudication will be analyzed using both results.

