Statistical Analysis	
For each treatment group, the proportion of subjects with and without biopsy-assessed cirrhosis at the end of study by baseline biopsy-assessed cirrhosis status will be presented in a shift table from Baseline to the end-of-study.
 
For the subset of subjects who were non-cirrhotic at Baseline, Kaplan-Meier (KM) estimates of the time to cirrhosis (as assessed by biopsy) will be summarized and graphed by treatment group.
 
For the subset of subjects who were cirrhotic at Baseline, cumulative incidence estimates of the time to improvement in fibrosis/cirrhosis (as assessed by biopsy) will be summarized and graphed by treatment group.

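### Kaplan-Meier curves that censor deaths overstate the absolute probability of transplant, HCC, liver-related death and the other components without all-cause death; cumulative incidence should be shown instead

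*Protocol*

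**What the plan says.** Section 13.1.8 (full text available in Version 3.1) compares OCA with historical controls on all-cause death, liver-related death, transplant, transplant or all-cause death, transplant or liver-related death, and HCC. It specifies a stratified log-rank test and a Cox hazard ratio and, without distinguishing among the six, that "KM estimates of the distribution of the time-to-event will be tabulated and graphed by treatment group". Medians are to be given where they can be estimated.

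Section 13.1.9.1 gives one rule for all time-to-event analyses: "subjects who do not experience an event will be censored at the time of their last contact".

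Section 13.1.5 covers OCA versus placebo in the ITT population. Its list includes the components of the primary endpoint, varices, liver-related death and composites built on liver-related death. It says: "The same analysis methodology as used for the primary efficacy analysis will be used for these secondary efficacy analyses". The Version 4 synopsis keeps that statement. It also takes HCC out of the primary composite and lists time to HCC as a secondary endpoint of its own.

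Cumulative incidence appears once, in the Appendix C biopsy sub-study, for improvement in fibrosis or cirrhosis among subjects cirrhotic at baseline. The same sub-study uses KM for time to cirrhosis.

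**The concern.** KM is right for the primary composite, for all-cause death, and for transplant or all-cause death, because no death is censored there. For the other endpoints a patient who dies can no longer have the event, or, for liver-related death, has died of something else. Censoring that patient treats the event as still possible later. The curve then describes a hypothetical population without those deaths, not the share of patients who actually have a transplant or HCC.

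The study is planned to last 10 years and all-cause death is itself a primary component, so competing deaths will occur. At stake is whether the absolute risks reported for secondary and supportive endpoints can be read as risks. A large registry control group does not help: it narrows the interval around the overstated figure.

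**Working it through.** **1. The plan's own figures.** Inputs from Section 13.1.2: "The 2 groups will be compared using a 2-sided log rank test at the 5% level of significance"; "placebo survival estimate of 0.6 at 8 years with a hazard ratio of 0.60"; "a total of 127 events (both groups combined) will provide 80% power"; "it is estimated that approximately 428 subjects will be enrolled to attain 127 events".

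- Schoenfeld: 4 × (1.960 + 0.842)² / (ln 0.6)² = 120.3, so 121 events. Freedman: (1.960 + 0.842)² × (1.6/0.4)² = 125.6, so 126.
- Lan-DeMets O'Brien-Fleming looks at 50%, 75% and 100% inflate these by 1.020, to 122.7 and 128.0. Power at 127 events is 81.3%.
- Uniform 4-year accrual, 10 years in total and exponential hazards give a mean event probability of 0.3308. Then 127/0.3308 = 384, and 384/0.90 = 427 with the 10% dropout stated in the Version 4 synopsis.

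The stated 127 and 428 are reproduced. The planned placebo composite hazard is −ln(0.6)/8 = 0.0639 per year.

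**2. Formulas.** With constant cause-specific hazards l (event) and c (competing death):

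- 1 − KM = 1 − exp(−l·t)
- cumulative incidence = l/(l + c) × [1 − exp(−(l + c)·t)]
- SE = √[F(1 − F)/n], with F = 1 − KM. This ignores other censoring, so it is a lower limit and the ratios to it are upper limits.

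**3. Assumptions not in the documents.** l is 5-30% and c is 10-50% of 0.0639; t is 6 to 10 years. Control-group sizes of 1000 to 12000 are illustrative: Section 13.1.1.1 gives only more than 6000 per database, before selection.

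| l, c (share of composite), t | 1 − KM | Cumulative incidence | Excess (points) | Relative |
|---|---|---|---|---|
| 5%, 10%, 6 y (smallest) | 1.90% | 1.86% | 0.04 | 1.9% |
| 20%, 30%, 8 y (middle) | 9.71% | 9.02% | 0.70 | 7.7% |
| 5%, 50%, 10 y (largest relative) | 3.14% | 2.69% | 0.45 | 16.7% |
| 30%, 50%, 10 y (largest absolute) | 17.43% | 15.00% | 2.43 | 16.2% |

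Excess in SE units of a single curve:

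| n | Range over the grid | Middle case |
|---|---|---|
| 214 | 0.04-0.94 | 0.34 |
| 1000 | 0.08-2.0 | 0.74 |
| 3000 | 0.14-3.5 | 1.29 |
| 6000 | 0.20-5.0 | 1.82 |
| 12000 | 0.29-7.0 | 2.57 |

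**4. Effect on the between-group difference.** In the middle case, multiply both OCA hazards by 0.6. The excess is 0.70 points in controls and 0.26 in OCA, so the difference is overstated by about 0.43 points. That is roughly 0.26 SE, because the OCA arm of 214 dominates the SE of the difference.

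**5. Do mortality differences distort the KM comparison?** Take l = 0.016 per year in both groups, with c = 0.020 in one and 0.030 in the other, at 10 years (all assumed). 1 − KM = 1 − exp(−0.16) = 14.8% in both. Cumulative incidence is (0.016/0.036) × (1 − exp(−0.36)) = 13.4% and (0.016/0.046) × (1 − exp(−0.46)) = 12.8%. The KM curves coincide; the cumulative incidence curves differ by 0.6 points through mortality alone.

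**The case against.** The strongest reply is that little depends on these curves. Section 13.1.8 is supportive, and Section 13.1.10 makes endpoints outside the hierarchy descriptive and exploratory. The log-rank test and Cox model remain valid as cause-specific comparisons. Raw numbers and percentages with events are reported beside the curves. Transplant or all-cause death, the outcome named for any revised primary analysis, is unaffected. A competing-risk display could be added in the SAP, and Version 4 Section 13.1.8 is not available to check. The Appendix C contrast is also weak, since that text does not name death as the competing event.

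All of this stands as a limit on importance. It does not remove the point: the protocol is not silent but names KM for these outcomes, and the Version 4 synopsis retains the method for the component endpoints.

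Three stronger readings are tempting and are not supported.

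- A reader might infer a definite size, such as 1 to 2.5 SE in the control group. The middle case gives 1.29 to 2.57 SE for n = 3000 to 12000, but the rates and n are assumed, and the grid runs from 0.08 to 7.0 SE for n = 1000 to 12000.
- A reader might infer that different background mortality in registry and trial patients would make KM curves mimic a treatment effect. Step 5 shows the reverse under constant hazards: 1 − KM does not contain the death hazard, and it is the cumulative incidence that shifts.
- A reader might place the hospitalization components in the historical comparison. They are not among its six outcomes and enter only through Section 13.1.5.

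**Conclusion.** The point holds for absolute risks. Four of the six historical-control outcomes are affected (liver-related death, transplant, transplant or liver-related death, HCC), as are the Section 13.1.5 endpoints that do not include all-cause death. Time to MELD score ≥15 in Section 13.1.4 shares the method, so its displayed curve is affected too, though its test in the hierarchy is not.

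The direction is certain whenever competing deaths occur. The size is 0.04 to 2.4 percentage points, about 2-17% relative, under the assumed hazards. It is below one SE in a randomized arm and larger in SE units for a large control group. The primary test, key secondary hierarchy, power and type I error do not change. This is a worthwhile correction to secondary and supportive displays, not a threat to the trial's main conclusion.

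**What to change.** In Sections 13.1.5 and 13.1.8, and for the MELD score ≥15 display in Section 13.1.4:

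- For every time-to-event endpoint that does not include all-cause death, present Aalen-Johansen cumulative incidence by group for absolute risks. Treat death from any cause outside the endpoint as a competing event, and transplant as well for events of the native liver.
- Keep the stratified log-rank test and Cox hazard ratio as the between-group comparison, labelled cause-specific.
- Show the cumulative incidence of death alongside, because cumulative incidence of transplant or HCC can differ between OCA and registry controls through mortality alone.
- Keep KM for the primary composite, all-cause death, and transplant or all-cause death.

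The cost is a wording change and one more standard display. No new data are needed. Reported percentages for the affected endpoints become slightly lower.

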7. INVESTIGATIONAL PLAN

7.1. Overall Study Design

This is a Phase 4, double-blind, randomized, placebo-controlled, multicenter study. Eligible subjects will have a diagnosis of PBC with bilirubin levels of $>ULN$ and $\leq 5 \times ULN$ and/or ALP $>3 \times ULN$. Subjects enrolled will be at higher risk of liver-related clinical complications.

Approximately 428 subjects meeting all enrollment criteria will be recruited into the study over an approximate 4-year period, randomly allocated to treatment with either OCA or matching placebo in a 1:1 ratio (Figure 1). Subjects will be screened during a 1 to 8-week Screening period prior to entering the study to allow for the collection of repeat serum chemistry samples (at least 2 weeks apart) to confirm pretreatment ALP and total bilirubin values (refer to Section 9.7.6). Randomization will be stratified by UDCA treatment (yes/no) and baseline bilirubin categories ($>ULN/\leq ULN$). In addition to the placebo control arm, multiple historical control groups (concurrent and retrospective) will be used.

Subjects will be dosed according to their cirrhosis status and Child-Pugh Score. Subjects who are non-cirrhotic or classified as Child-Pugh A at Screening will initiate investigational product once daily with 5-mg OCA or matching placebo. Following 3 months of once daily treatment with investigational product, the dose should be titrated to a maximum 10 mg OCA or matching placebo once daily, based on tolerability and biochemical response (see Section 7.3).

[figure not shown]
Subjects with cirrhosis (see Section 9.7.3) and classified as Child-Pugh Class B or Child-Pugh Class C will follow a modified dosing regimen, and will initiate investigational product once weekly with the 5-mg OCA or matching placebo dose. In addition, these subjects will follow a modified titration plan, which is outlined in Appendix A.

It is anticipated that subjects will be followed for a minimum of approximately 6 years. The study will continue until approximately 127 adjudicated primary endpoint events have been accrued in unique subjects, or until the Sponsor (eg, based on advisement by the Data Monitoring Committee; DMC) terminates the study.

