13.1. Efficacy Analysis

13.1.1. Analysis Populations

The following subject populations will be evaluated and used for presentation and analysis of the data:

- The Intent-to-Treat (ITT) Population will include all randomized subjects who receive any amount of investigational product (OCA or placebo). The ITT Population will be the primary population used for efficacy analyses. Treatment assignment will be based on the randomized treatment.
- The Safety Population will include all subjects who received any amount of investigational product (placebo or OCA). The Safety Population will be the primary population used for safety analyses. Treatment assignment will be based on the treatment actually received.
- The PK population will include all OCA subjects who have at least one confirmed fasted analyzable sample. Subjects must have been fasting for approximately 8 hours prior to the visit and must not have any major protocol deviations that potentially affect exposure levels. The PK population will be used for OCA PK analyses.
- The Overall Historical Control Population will include subjects from the United Kingdom (UK) -PBC Group and Global PBC Study Group databases with demonstrated comparability to randomized subjects in this clinical study (747-302) with respect to both subject characteristics and disease progression.
- The UK-PBC Historical Control Population will include subjects from the UK-PBC Group databases with demonstrated comparability to randomized subjects in this clinical study (747-302) with respect to both subject characteristics and disease progression.
- The Global PBC Historical Control Population will include subjects from the Global PBC Study Group database with demonstrated comparability to randomized subjects in this clinical study (747-302) with respect to both subject characteristics and disease progression.

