13.1.1.1. Comparability of Historical Controls

Utilization of both historical control/observational databases (UK-PBC and Global PBC Study Group), with more than 6000 subjects each, allow for a rigorous subject level meta-analysis. The historical databases include long-term follow up, detailed subject-level information such as baseline clinical characteristics, longitudinal liver biochemistry, and long-term outcomes, and

span a broad range of subject characteristics that may influence disease (disease state, age, gender, and regional differences in standard of care). Historical controls from both databases will be chosen based on the same study inclusion/exclusion criteria where possible.

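### The historical-control hazard ratio is stratified by randomization strata while its log-rank test is stratified by propensity quintile, so the reported effect lacks the propensity adjustment and can be confounded

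*Protocol*

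**What the plan says.** Protocol Section 13.1.8 estimates propensity scores by logistic regression, cuts them at quintiles, and states: "The propensity score quintile will be then be used as the stratification factor in the stratified log rank test". The comparison is randomized OCA subjects against the Overall Historical Control Population, for six outcomes built from death, liver transplant and hepatocellular carcinoma. The paragraph after the outcome list turns to estimation: "The hazard ratio and 95% CI will be determined based on a Cox regression model stratified by randomization strata". Section 13.1.3 prescribes the same Cox stratification for the randomized primary analysis.

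Section 7.1 defines the randomization strata: "Randomization will be stratified by UDCA treatment (yes/no) and baseline bilirubin categories", that is, four cells.

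Section 13.1.8 itself argues that matching can mitigate bias only if it considers the full range of covariates on which the treated subjects and the historical controls might differ. It leaves the covariate list to the SAP, but it fixes the Cox stratification in the protocol.

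The three historical control populations in Section 13.1.1 consist of database subjects "with demonstrated comparability to randomized subjects in this clinical study (747-302) with respect to both subject characteristics and disease progression". Section 13.1.1.1 gives a different selection rule: "Historical controls from both databases will be chosen based on the same study inclusion/exclusion criteria where possible".

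**The concern.** A non-randomized comparison depends on its adjustment. Here the p-value carries the propensity adjustment, and the hazard ratio and confidence interval, which are what readers will quote, do not. The two could disagree: a hazard ratio well away from 1 beside an unremarkable p-value, or the reverse, with no way to tell treatment effect from imbalance.

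The stakes are more than cosmetic. Section 5.5.2.3 offers the historical comparison as a possible help against bias in the placebo arm, for example from uptake of commercial OCA. Section 13.1.8 also lets the DMC recommend a revised primary analysis of transplant or death against pooled placebo and historical controls, using similar methodology and subject to prior regulatory agreement. The same mismatch could then reach a primary estimate.

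**Working it through.** **1. Can the Cox model be fitted as written?** Historical controls carry no randomization stratum, and no section shown assigns them one. A stratified Cox model estimates the treatment effect only within strata that contain both groups. If controls are left without a stratum, or put in one of their own, no stratum contains both groups and the effect cannot be estimated. The only workable reading is that UDCA use and bilirubin category are derived from the controls' baseline data. The rest assumes that reading, which is the one most favourable to the plan.

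**2. What is then adjusted for?** The test uses quintiles of a score built on the covariates to be listed in the SAP. The estimate uses four cells from two binary factors. Anything else in the score, including variation in bilirubin within a category, is left unadjusted in the hazard ratio.

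**3. Size.** The plan states no figure for this comparison, so there is none to reproduce. The following is an illustration.

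Inputs from the Protocol:
- 428 subjects randomized 1:1, so 428 / 2 = 214 on OCA (Section 13.1.2).
- Event-free probability of 0.6 at 8 years under placebo, exponential, so hazard = -ln(0.6) / 8 = 0.0638 per year. This is the composite-endpoint rate, borrowed as a baseline.
- Follow-up uniform between 6 and 10 years, from 4 years of accrual and 6 of follow-up.

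Assumed inputs:
- 1,500 controls, and a true hazard ratio of 1.
- UDCA use 93% (OCA) and 85% (controls), hazard ratio 0.7; bilirubin above ULN 50% and 35%, hazard ratio 2.
- One further measured covariate, included in the propensity model, with hazard ratio 1.3 or 1.6 per SD and a mean in the OCA group shifted by -0.5 to +0.5 SD.

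First-order expectation when that covariate is unadjusted: false HR = exp(shift × ln(HR per SD)). For example, exp(-0.5 × ln 1.6) = exp(-0.235) = 0.79.

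Simulation (20 replicates per row; Monte Carlo standard error of the mean log hazard ratio 0.02 to 0.03 for the randomization-strata model):

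| HR per SD | Shift (SD) | First-order false HR | Cox, randomization strata | Cox, propensity quintiles |
|---|---|---|---|---|
| 1.3 | -0.50 | 0.88 | 0.87 | 0.99 |
| 1.3 | -0.25 | 0.94 | 0.93 | 0.98 |
| 1.3 | 0 | 1.00 | 1.02 | 1.03 |
| 1.3 | +0.25 | 1.07 | 1.10 | 1.04 |
| 1.3 | +0.50 | 1.14 | 1.13 | 1.02 |
| 1.6 | -0.50 | 0.79 | 0.80 | 0.99 |
| 1.6 | -0.25 | 0.89 | 0.90 | 1.01 |
| 1.6 | 0 | 1.00 | 0.99 | 0.99 |
| 1.6 | +0.25 | 1.12 | 1.11 | 1.03 |
| 1.6 | +0.50 | 1.26 | 1.31 | 1.08 |

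The randomization-strata model follows the unadjusted expectation. Quintiles remove most of the distortion but not all of it. A covariate missing from the propensity model and unrelated to its covariates would be removed by neither.

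**The case against.** Much can be said for the plan. The comparison is supportive and evaluated separately from the placebo comparison; Section 13.1.10 makes analyses outside its hierarchy descriptive and exploratory. The randomized primary result is untouched unless the revised-primary route is taken. The p-value remains propensity-stratified. UDCA use and bilirubin are not trivial factors, and the eligibility criteria remove some imbalance before any model is fitted. No imbalance is documented, so the sizes above show what can happen, not what will. All of this stands. It limits the consequence but does not reconcile the two stratifications, and nothing in the text shown does.

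The quoted sections belong to Version 3.1. Version 4's contents list keeps a Section 13.1.8, and its synopsis keeps the historical populations and the historical comparison, but its Section 13 is not shown. Whether the sentence survives cannot be checked here.

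A reader might also infer from Section 13.1.1 that controls are selected on their outcome, because disease progression is named separately from subject characteristics and Section 6.2 treats it as something OCA may affect. The documents do not establish this. The term is undefined and can mean how advanced the disease is at entry. Sections 13.1.1.1 and 13.1.8 select controls by the trial's eligibility criteria where possible. On the score itself the plan says: "Only covariates and not outcome variables will be included in the propensity score estimation". No section shown describes screening controls on their post-baseline course. The phrase is ambiguous, and clarifying it is enough.

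**Conclusion.** The mismatch is real and wrong as written: the hazard ratio and confidence interval omit the adjustment that Section 13.1.8 says the comparison needs, and they refer to strata that the controls do not have. It is too strong to say that the estimate is confounded. It can be, in either direction, to the extent that covariates other than UDCA use and bilirubin category differ between the groups.

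Under the assumed inputs and no true effect, the false hazard ratio runs from about 0.80 to 1.31, against 0.98 to 1.08 with quintiles; without imbalance both models give 0.99 to 1.03. These ranges rest on the assumed covariate strength, imbalance and control numbers, none of which the Protocol supplies. No event count, sample size or primary-analysis figure changes.

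**What to change.** In Section 13.1.8, for the historical-control comparison, replace the randomization strata in the Cox sentence with the propensity score quintiles, the same strata as the log-rank test. Make sure that any revised primary analysis built on that section inherits the corrected wording. Check Version 4's Section 13.1.8 and the SAP for the same sentence.

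As a secondary clarification, in the three historical-control definitions of Section 13.1.1 replace disease progression with baseline disease stage, so that the definitions agree with the eligibility-based selection in Sections 13.1.1.1 and 13.1.8. The time at which baseline is taken for a historical control should be fixed with it, in the SAP if it is not there already.

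The cost is a few words in the protocol and SAP. No data, visits or patients are added.
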